## Effect of serum hormone levels and CCP on disease progression

A logistic regression model will be run to determine whether final measurements of testosterone, FSH and LH, or final CCP score has an effect on overall disease progression (progression by *any* measure). It will be adjusted by the baseline measurements.

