# Secondary Endpoints

The secondary endpoints involve measures of disease progression from baseline to 12 months, assessed by serial multi-parametric magnetic resonance imaging (MRI) of the prostate, serum PSA measurement, and prostate biopsy.

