## Biochemical disease progression

Biochemical disease progression (or regression) will be defined as a 50% increase (or decrease) in serum PSA at 12 months from baseline.

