## Serum hormone levels

Levels of serum testosterone, Follicle Stimulating Hormone (FSH), and Luteinizing Hormone (LH) will be measured every 6 months. Analyses will focus on whether serum levels have an effect on disease progression, and whether the serum concentrations differ between treatment arms.

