### Cell Cycle Progression (CCP) Score

Biopsy samples taken pre-study and at 12 months will be used for CCP score analysis. Exploratory analyses will investigate how the change in CCP score differs between treatment arms and whether CCP score has an effect on disease progression.

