## Study period and visits

The study will last for 18 months (plus ≥30 days for pharmacovigilance). Data will be collected at 3-monthly intervals. Secondary endpoint measures will be carried out at the following times:

- MRI taken at baseline and 12 months
- Prostate biopsy at baseline and 12 months for pathology review & CCP score analysis.
- Serum PSA measured at baseline and every 3 months until 18 months
- Serum testosterone, FSH, and LH at baseline and every 6 months until 18 months
- Serum vitamin D3 taken at baseline and every 6 months until 18 months
- Serum calcium at screening and 6, 12, and 18 months

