### Change in serum hormone levels and CCP score

The effect of treatment on testosterone, FSH, LH, and CCP will be investigated using an ANOVA model. The difference in serum hormone concentration from baseline to 18 months for each of the hormones, or the difference in CCP score from baseline to 12 months will act as the dependent variable. Treatment will be the independent variable, and a treatment interaction term may also be added. The hormone concentrations will be log-transformed, as with PSA.

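### The model relating hormones to progression gives no month for the 'final' hormone values; the most natural reading, month 18, falls six months after the 12-month outcome

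*SAP*

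**What the plan says.** The model in question is under the SAP's supplementary analyses, in Effect of serum hormone levels and CCP on disease progression. It is a logistic regression, adjusted for baseline measurements, to determine "whether final measurements of testosterone, FSH and LH, or final CCP score has an effect on overall disease progression", where overall progression means progression by any measure. No month is attached to the word final.

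The timing of the outcome is given elsewhere in the SAP:

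- Secondary Endpoints describes them as "measures of disease progression from baseline to 12 months".
- Biochemical disease progression defines the PSA component as "a 50% increase (or decrease) in serum PSA at 12 months from baseline".
- Study period and visits has "MRI taken at baseline and 12 months", and prostate biopsy at the same two times.
- Model 5, on progression by any measure, combines tumour volume, PSA and Gleason score.

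The timing of the predictors is given as follows:

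- Study period and visits schedules "Serum testosterone, FSH, and LH at baseline and every 6 months until 18 months".
- Change in serum hormone levels and CCP score, directly before the model in question, analyses "The difference in serum hormone concentration from baseline to 18 months for each of the hormones", but takes CCP change only to 12 months.
- Cell Cycle Progression (CCP) Score states: "Biopsy samples taken pre-study and at 12 months will be used for CCP score analysis".

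The question is not incidental to the hormone work. Serum hormone levels states: "Analyses will focus on whether serum levels have an effect on disease progression".

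**The concern.** A regression meant to show that a hormone level affects progression needs the level to be measured no later than the progression, and preferably before it. If the final hormone value is the month-18 sample, the order is reversed. Progression status is settled at month 12, and the hormone value is drawn six months later. Anything that followed the 12-month result and bears on hormone levels would then appear in the model as if the hormone had influenced progression. Adjusting for the baseline hormone value does not help, because baseline cannot account for a change that arises after month 12.

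Two further consequences follow. A man who leaves the study between months 12 and 18 has a progression outcome but no month-18 predictor, so a strict month-18 model loses him. And because the SAP does not name the month, two analysts could follow it faithfully and fit different models.

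**Working it through.** The SAP gives no figure to reproduce here. The check is a comparison of timelines.

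**Outcome and predictor side by side**

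| Item | Time points | SAP section |
|---|---|---|
| MRI component of progression | 0, 12 | Study period and visits |
| Biopsy (Gleason) component | 0, 12 | Study period and visits |
| PSA component | 12 against 0 | Biochemical disease progression |
| Testosterone, FSH, LH sampling | 0, 6, 12, 18 | Study period and visits |
| Hormone change analysis | 0 to 18 | Change in serum hormone levels and CCP score |
| CCP score | pre-study, 12 | Cell Cycle Progression (CCP) Score |
| Final hormone value in this model | not stated | Effect of serum hormone levels and CCP on disease progression |

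All three components of the outcome are fixed at month 12. No section moves progression to month 18, and none defines the final hormone value as the month-12 one.

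**Gap between predictor and outcome, for each hormone value that could be used**

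- Month 18: 18 − 12 = 6 months after the outcome.
- Month 12: 12 − 12 = 0, concurrent with the outcome.
- Month 6: 12 − 6 = 6 months before the 12-month assessment.
- Final CCP score: 12 − 12 = 0, concurrent. The time reversal therefore concerns the hormones only.

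**Men with an outcome but no month-18 value**

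The SAP gives no drop-out rate. Assume 102 men (the planned number), a constant drop-out hazard, and a proportion q lost by month 18, with q = 10, 20 or 30%. The number remaining at month 12 but gone by month 18 is 102 × [(1 − q)^(12/18) − (1 − q)]:

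- q = 0.10: 102 × (0.932 − 0.900) = 3.3
- q = 0.20: 102 × (0.862 − 0.800) = 6.3
- q = 0.30: 102 × (0.788 − 0.700) = 9.0

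**If final means last available**

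On the same assumptions, the share of men present at month 12 who go on to give a month-18 value is (1 − q) / (1 − q)^(12/18) = (1 − q)^(1/3), that is 0.965, 0.928 and 0.888. So for roughly nine in ten or more of the men with an outcome, the predictor is still the month-18 value. For the others it is an earlier one, and the month then varies between patients. This reading keeps the 3 to 9 men in the model but leaves the reversed order in place for most.

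**The case against.** The strongest reply is that month 18 is only an inference, and the SAP contains evidence for month 12. In the same sentence the final CCP score is a 12-month value. The preceding section writes out 18 months for the hormones, whereas this section chooses a different word. The supplementary analysis of serum vitamin D3, the nearest parallel of a serum marker set against a disease measure, relates it to PSA at 12 months, although both are sampled to month 18. If final means month 12, there is no gap.

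This stands to the extent that a reader should not infer that the SAP expressly places the hormone values at month 18. It does not. What remains is that the SAP leaves the month open, and that its sampling schedule and the adjacent hormone analysis both point to 18.

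A reader might also infer that the month-18 value produces a known excess of false-positive results which the month-12 value would avoid. The documents do not support that. They give no hormone variability, no progression rate and no size for any hormone change after progression. A comparison in which the change occurs only after month 12 favours the month-12 value by construction. Since progression develops between baseline and month 12, some of the change could already be present by then.

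Finally, a reader might extend the point to the drop-out models under Survival analysis that include progression. Bias there would require progression to be a covariate fixed from time zero and men without a 12-month assessment to be coded as non-progressors. The SAP states neither, so this is not part of the point.

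**Conclusion.** The point holds as a minor defect. The month of the final hormone values is not stated. On the most natural reading the predictor is measured six months after an outcome it is said to affect, and a last-available reading changes this for few men. An association found that way may reflect what followed progression, so it could not be reported as an effect of hormone level.

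The six-month gap rests only on the SAP's own schedule and on reading final as month 18. The loss of about 3 to 9 men rests in addition on a strict month-18 reading, assumed drop-out of 10 to 30% and a constant hazard. No size can be put on the bias itself from the document.

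The analysis is supplementary. The recruitment endpoint and the main treatment comparisons do not use these hormone values and are unaffected.

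**What to change.** In Effect of serum hormone levels and CCP on disease progression, replace the reference to final hormone measurements with the 12-month testosterone, FSH and LH values, adjusted for baseline. This puts them at the same time as the 12-month CCP score. State that the hormone and CCP results will be reported as associations with progression, not as effects on it.

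The month-6 hormone value, adjusted for baseline, may be added as a further analysis. It is the only scheduled post-baseline value that precedes the 12-month assessment.

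The cost is a change of SAP wording. Both samples are already scheduled, so no visit or test is added. There is a limit to what the change achieves: the 12-month value is concurrent with the outcome, so using it removes the time reversal but not all reverse causation.

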## Disease progression by logistic regression

Five logistic regression models will be run to determine the effect of treatment on disease progression. For all models aspirin (0 = placebo, 1 = 100mg, 2 = 300mg) and vitamin D3 (0 = placebo, 1 = active) will be used as predictors. The main analysis will be unadjusted for covariates but secondary analyses will be adjusted for age, BMI, serum hormone levels (testosterone, FSH, LH), and CCP score. An interaction term between aspirin and vitamin D3 will be included in some secondary analyses. Also included will be a trend test p-value for the 3 aspirin treatments.

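### The supplementary model of final hormone levels and CCP score on progression leaves out the randomised treatments, so a treatment effect can be read as a marker effect

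*SAP*

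**What the plan says.** The model is in the SAP section Effect of serum hormone levels and CCP on disease progression. Its description begins, in part: "A logistic regression model will be run to determine whether final measurements of testosterone, FSH and LH, or final CCP score has an effect on". The outcome named there is progression by any measure. One adjustment is given: "It will be adjusted by the baseline measurements". Treatment is not mentioned.

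Two other sections make treatment a possible cause of both sides of this regression.

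- The section Disease progression by logistic regression opens with this statement: "Five logistic regression models will be run to determine the effect of treatment on disease progression". There the treatments are always included: "For all models aspirin (0 = placebo, 1 = 100mg, 2 = 300mg) and vitamin D3 (0 = placebo, 1 = active) will be used as predictors". That rule governs the five numbered models that follow it. The marker model is not one of them.
- The section Change in serum hormone levels and CCP score states its purpose in these words: "The effect of treatment on testosterone, FSH, LH, and CCP will be investigated using an ANOVA model".

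Behind the marker model lie aims that are posed as open questions. For hormones the SAP asks "whether serum levels have an effect on disease progression, and whether the serum concentrations differ between treatment arms". For CCP it says "Exploratory analyses will investigate how the change in CCP score differs between treatment arms and whether CCP score has an effect on disease progression".

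**The concern.** The final marker value is measured after randomisation. If aspirin or vitamin D3 shifts the marker, and also changes progression by a route that does not pass through that marker, treatment is a common cause of predictor and outcome. A model without treatment then assigns part of the treatment effect to the marker.

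Baseline adjustment does not remove this. It takes out stable differences between men and leaves the change since randomisation, which is the part that treatment acts on, so the bias grows.

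At stake is the answer to one of the two questions the SAP asks about each marker: does it affect progression? The error is largest where a treatment works and also moves the marker. Unlike most confounders, this one is randomised and known for every man.

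**Working it through.** **The plan's own figures.** The SAP gives no effect size, variance or power for this model. Its only power figure is the 89% for the recruitment rate. It reproduces (0.878 exact, 0.889 arcsine, 0.896 normal approximation) but has no bearing here. The sizes below therefore rest on assumptions.

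**Inputs from the SAP.** 102 men; a 3x2 factorial, so 2/3 of men on active aspirin and 1/2 on active vitamin D3.

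**Assumed.**
- Marker SD 1 within arm; correlation 0.7 between baseline and final value.
- No true marker effect on progression.
- Progression 45-50% without active treatment.
- Treatment shifts the final marker by *d* SD and multiplies the odds of progression by OR.
- All 102 men have a final marker value and a progression outcome.

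**Approximation.** Given baseline, the final marker has within-arm variance 1 − 0.7² = 0.51. Let *v* be the variance of the treatment indicator: 1/2 × 1/2 = 0.25 for vitamin D3 and 2/3 × 1/3 = 0.222 for active aspirin. The two are independent by design, so *v* = 0.472 when both act with the same *d* and OR. The spurious log odds ratio per SD is about

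ln(OR) × *d·v* / (0.51 + *d²·v*).

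Vitamin D3 alone, *d* = 0.5, OR = 0.5: 0.125 / (0.51 + 0.0625) = 0.218; 0.218 × (−0.693) = −0.151; exp(−0.151) = 0.86.

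Both treatments, *d* = 1, OR = 0.5: 0.472 / 0.982 = 0.481; 0.481 × (−0.693) = −0.333; exp(−0.333) = 0.72.

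**Simulation.** The model as written (final and baseline marker) was fitted to simulated trials of 102 men, about 3,000 per scenario. Ranges are across repeat simulations.

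| Scenario | Approximate OR per SD | Simulated OR per SD | False positives at 5% |
|---|---|---|---|
| Vitamin D3 alone, 0.25 SD, OR 0.67 | 0.95 | 0.95 | 5% |
| Vitamin D3 alone, 0.5 SD, OR 0.5 | 0.86 | 0.85 | 7.4-7.8% |
| Vitamin D3 alone, 1 SD, OR 0.5 | 0.80 | 0.79 | 15.5-16% |
| Both, 0.5 SD, OR 0.5 each | 0.77 | 0.76-0.77 | 14-15% |
| Both, 1 SD, OR 0.5 each | 0.72 | 0.71-0.72 | 30-32% |

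A separate set-up, with aspirin alone active and 40% progression on placebo, gave 7.5% (0.5 SD, OR 0.5), 10.1% (0.5 SD, OR 0.33), 14.4% (1 SD, OR 0.5) and 27.6% (1 SD, OR 0.33).

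**When there is no bias.** In the aspirin set-up, a shift in the marker with no effect on progression gave 4.4% false positives. An effect on progression with no shift in the marker gave 4.8%. The odds ratio was 0.99 in both.

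**Effect of baseline adjustment.** Without it, 0.51 in the formula becomes 1. For vitamin D3 at 0.5 SD: 0.125 / 1.0625 = 0.118, giving exp(−0.082) = 0.92 (simulated 0.93), against about 0.85 with baseline in the model.

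**With treatment added.** Across scenarios the marker's odds ratio returns to 0.98-1.03 and the false-positive rate to about 4-6%. If the three hormones share one model (three final values, three baselines, three treatment terms), simulation gave 0.99-1.01 and 5.5-6.0%.

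**Precision.** Treatment terms remove the treatment-driven part of the marker's variance, so its standard error rises by at least √((0.51 + *d²·v*)/0.51). For vitamin D3 alone that is √(0.5725/0.51) = 1.06 at 0.5 SD and √(0.76/0.51) = 1.22 at 1 SD. Simulation, which also pays for the extra terms, gave about 10% and 27%, and about 15-45% if both treatments shift the marker.

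**The case against.** The strongest reply is that the SAP already fits treatment and markers together. Secondary versions of its five models, including progression by any measure, say that "secondary analyses will be adjusted for age, BMI, serum hormone levels (testosterone, FSH, LH), and CCP score". This is true and matters: a treatment-adjusted marker estimate may come out of those fits. It does not replace the marker model. Those models are set up to estimate the treatment effect, do not say at which visit the covariates are taken, and do not pair final with baseline values. Nothing tells the analyst to prefer them for the marker question.

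Second, a reader might infer that the SAP expects treatment to move both marker and progression. The text does not support that. It asks whether hormones differ by arm, calls the CCP work exploratory, and gives no direction or size. The bias is conditional on both effects being present.

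Third, the larger figures need a full 1 SD shift together with halved odds of progression. That is fair: nothing in the SAP makes such effects likely.

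Fourth, with 102 men the fix partly trades bias for variance. For vitamin D3 at 0.5 SD and OR 0.5, the root-mean-square error of the marker's log odds ratio was 0.33 without and 0.32 with treatment. In the weak scenario it was 0.29 without and 0.32 with. This stands as a cost. What the fix buys is a test near its nominal level and an estimate that does not absorb the treatment effect.

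Fifth, adding treatment does not make the marker term causal. The SAP measures hormone change to 18 months while progression is assessed at 12, so a final hormone value may come after the outcome. That is a separate matter, which this fix leaves open.

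**Conclusion.** The point holds as a conditional one. The marker model omits the randomised treatments, and baseline adjustment does not protect it. If treatment both shifts a marker and alters progression by another route, a marker with no effect shows an odds ratio per SD of about 0.85 with 8% false positives for moderate effects of one treatment, and up to about 0.72 with 30% for large effects of both. If effects are weak, or only one of the two links exists, there is no material bias. All effect sizes, the correlation of 0.7 and the progression rate are assumptions.

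It would go too far to say that any marker association found by this model is spurious, or that the trial's conclusions are at risk. The main objective is recruitment feasibility, the analysis stands among the supplementary ones, and no sample size or treatment claim in the SAP depends on it. Severity is minor. The bias does not shrink with sample size: if the same model were reused with the 800 men foreseen for the definitive trial, the four aspirin-only scenarios give false-positive rates of 27% to 95%. The SAP does not say it will be reused.

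**What to change.** In the section on the effect of serum hormone levels and CCP on disease progression, state that aspirin (placebo, 100mg, 300mg) and vitamin D3 (placebo, active) enter the model as predictors next to the final and baseline marker values. If the model without treatment is kept, report it only alongside this one.

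The cost is one sentence and three model terms (two for aspirin, one for vitamin D3), with no new data. The marker's standard error rises by roughly 10% (0.5 SD shift) to 27% (1 SD shift) if vitamin D3 alone moves the marker, and by about 15-45% if both treatments do. The test of the marker keeps about its 5% level.

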### Pathology review

Consistency of pathology reporting will be assessed by the proportion of reviewed biopsy results in agreement with the original result. Any disagreements will be presented and will include the reasons such as Gleason pattern and/or score, as well as any possible changes to diagnoses.

### Serum vitamin D3 and calcium

The median corrected serum calcium level will be reported for each treatment arm, as well as the proportion of samples >2.65mmol/L (hypercalcaemic). The relationship between serum vitamin D3 and PSA level at 12 months will be quantified using a linear regression model, with log(1+PSA) as the dependent variable. Baseline PSA and serum vitamin D3 measures will be included to adjust for differences between patients.

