## Sample size

Sample size calculations suggested that 800 men are needed for a future definitive randomised chemoprevention study of standard (300mg) or low dose (100mg) aspirin vs. placebo and/or Vitamin D3 vs. placebo in patients enrolled on an Active Surveillance programme for prostate cancer.

This feasibility trial aims to demonstrate the acceptability and viability of recruitment for this larger study. Data from this trial will be used to determine the number of centres required to enable the larger, 800 patient trial to fully recruit within 4 years. The sample size was chosen to examine acceptance rates and the time required to recruit 102 patients. We plan to recruit 102 patients over 18 months. If the true recruitment rate is 33.3%, approaching 300 individuals, and therefore recruiting ≥100, would achieve 89% power to show that the true recruitment rate is above 25% (using a two-sided binomial proportion test with a 0.05 significance level).

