# Randomisation procedure

The randomisation will be by permuted block randomisation in order to achieve approximate balance across the 6 treatment groups. This randomisation scheme consists of a sequence of blocks such that each block contains a pre-specified number of treatment assignments in random order, for example each treatment occurring twice in a block. The purpose of this is so that the randomisation scheme is balanced at the completion of each block. PROVENT has 3x2 treatment combinations (a block of 6). However, there are two sizes of placebo aspirin to match the active drug: small (100mg size) and large (300mg size) providing an added complication, as this effectively produces eight possible combinations. To maintain the correct balance of drug and placebo, the PROVENT feasibility study will use two blocks of 6 to make a 'Superblock' of 12. In one block of 6 the placebo aspirin will be first small and then large, and in the other block they will be first large and then small. This ensures the correct number and size of placebo aspirin are dispensed, and that all 8 treatment combinations are represented in each superblock. Consequently, twice as many aspirin, as placebo aspirin tablets, are required for the trial.

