#### Serum vitamin D3 and calcium

Levels of serum vitamin D3 and serum calcium will be measured at baseline, 6, 12, and 18 months. Hypercalcaemia (corrected serum calcium > 2.65mmol/L) is a well-known symptom of chronic vitamin D3 overdose.

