## Safety endpoints

Toxicity data will be presented as the proportion of patients displaying either mild, moderate, or severe symptoms split by treatment *group* (aspirin: placebo, 100mg, 300mg; vitamin D3: placebo, active). Serious adverse events data will be presented as the proportion of mild, moderate and severe events recorded by treatment group.

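### Hypercalcaemia is summarised per sample, so the planned figure cannot show how many men became hypercalcaemic, and the plan does not say whether the pre-treatment sample counts

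*SAP*

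**What the plan says.** The SAP has two sections headed Serum vitamin D3 and calcium. The one among the endpoint definitions gives the schedule, "Levels of serum vitamin D3 and serum calcium will be measured at baseline, 6, 12, and 18 months", and the reason for measuring calcium: "Hypercalcaemia (corrected serum calcium > 2.65mmol/L) is a well-known symptom of chronic vitamin D3 overdose". Study period and visits gives the same four time points but places the first at screening: "Serum calcium at screening and 6, 12, and 18 months". On either wording, one sample precedes treatment and three follow it.

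The section of the same name under Supplementary analyses sets the analysis. "The median corrected serum calcium level will be reported for each treatment arm", and the sentence continues "as well as the proportion of samples >2.65mmol/L (hypercalcaemic"). It names no visit, does not say how the pre-treatment sample is handled, and gives no count of men with a raised value.

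Safety endpoints uses the patient as its unit: "Toxicity data will be presented as the proportion of patients displaying either mild, moderate, or severe symptoms", split by aspirin group and by vitamin D3 group. It does not mention laboratory calcium.

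**The concern.** The SAP links raised calcium to vitamin D3 overdose, so this is a safety summary. The natural question is how many men on active vitamin D3 became hypercalcaemic after starting, compared with placebo. A proportion of samples answers a different question, namely how often a raised value turns up among the samples taken. One man raised at three visits and three men raised once each contribute equally to it.

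Two further matters follow from the wording. A reader of the final table would not know whether the denominator includes a sample that treatment could not have affected. And if visits are pooled, a man who leaves after month 6 supplies two samples where a man who completes supplies four, so early leavers carry less weight. The SAP plans an analysis of early drop-out, so some is expected.

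What is at stake is the clarity of the vitamin D3 safety report from a study meant to inform a definitive trial of 800 men with the same vitamin D3 comparison.

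**Working it through.** The SAP gives no expected rate of hypercalcaemia, so there is no figure of its own to reproduce here.

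**Inputs from the SAP**
- Planned size: "We plan to recruit 102 patients over 18 months" (Sample size).
- Allocation: "approximate balance across the 6 treatment groups" (Randomisation procedure). Three of the six groups are at each vitamin D3 level, so men per level = 102 / 2 = 51.
- Samples per man: 1 pre-treatment + 3 on treatment = 4.

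**Assumed for illustration:** complete sampling and 6 raised on-treatment samples in one vitamin D3 group.

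**Step 1. Denominators per vitamin D3 level**
- All samples: 51 × 4 = 204.
- On-treatment samples: 51 × 3 = 153.
- Pre-treatment share: 51 / 204 = 25%.

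**Step 2. How many men do 6 raised samples represent?** A man can have one to three raised on-treatment samples, so the number of affected men lies between 6 / 3 = 2 and 6 / 1 = 6.

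| Raised samples per affected man | Men affected | Per man | Per on-treatment sample | Per sample, all four visits |
|---|---|---|---|---|
| 3 | 2 | 2/51 = 3.9% | 6/153 = 3.9% | 6/204 = 2.9% |
| 2 | 3 | 3/51 = 5.9% | 6/153 = 3.9% | 6/204 = 2.9% |
| 1 | 6 | 6/51 = 11.8% | 6/153 = 3.9% | 6/204 = 2.9% |

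The two right-hand columns do not move while the per-man figure triples. Excluding the pre-treatment sample does not cure this, because the unit itself is the problem.

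**Step 3. Effect of including the pre-treatment sample, if all samples are pooled.** With normal pre-treatment values, the pooled proportion is 153 / 204 = 0.75 of the on-treatment proportion. Take 6 raised on-treatment samples on active and 1 on placebo (assumed):
- Difference, on treatment: 6/153 − 1/153 = 5/153 = 3.3 percentage points.
- Difference, all samples: 6/204 − 1/204 = 5/204 = 2.5 percentage points.
- Ratio: 6 / 1 = 6.0 either way.

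The ratio changes only if some pre-treatment values are raised. With one such sample in each group it becomes (6 + 1)/(1 + 1) = 3.5; with two, (6 + 2)/(1 + 2) = 2.7.

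**Step 4. Drop-out.** If a fraction d of men leave after the month 6 sample, samples per man average 1 + 1 + 2(1 − d) = 4 − 2d, and the pre-treatment share is 1/(4 − 2d). That gives 25% for d = 0, 28% for d = 0.2 and 31% for d = 0.4 (assumed rates).

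**The case against.** The strongest reply is that the SAP does not say that visits are pooled or that the pre-treatment sample is included. The wording is compatible with a table by visit. At a single visit, with one scheduled sample per man, the proportion of samples equals the proportion of men sampled. This stands: on both matters the SAP is silent, so Step 3 is conditional on one reading. It does not remove the main point, since per-visit proportions still do not give the number of men who were ever raised.

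A second reply is that affected men could appear in the per-patient toxicity table. That is possible, and the protocol, which is not shown, may settle it. But the SAP describes that table in terms of graded symptoms and does not name calcium.

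Two stronger readings are tempting. A reader might infer that the analysis treats repeated samples from one man as independent and so overstates precision. No interval or test is planned for the calcium summary, so there is no stated precision to criticise. A reader might also infer that the comparison between vitamin D3 groups is diluted on every scale. With complete data and normal pre-treatment values, only the absolute figures are; the ratio is intact.

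Finally, a count of men ever raised has its own weakness: men who stop early have fewer chances to be counted. That is correct, and the fix has to allow for it.

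**Conclusion.** The concern holds in a limited form. The SAP fixes the sample as the unit for hypercalcaemia and nowhere specifies a per-man count, so the planned figure cannot show how many men were affected. In the illustration, one reported value is compatible with 3.9% to 11.8% of men. The SAP also leaves open whether the pre-treatment sample is in the denominator. If it is, absolute proportions and differences fall to three quarters of their on-treatment values when pre-treatment calcium is normal.

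These sizes rest on 51 men per vitamin D3 level, complete sampling and assumed numbers of raised samples. The loss of the per-man count does not depend on them, provided that some men may be raised more than once. The matter is minor: it concerns one descriptive safety summary in a feasibility study, and neither the primary endpoint nor any stated test or decision rule depends on it.

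**What to change.** In the calcium paragraph under Supplementary analyses, replace the per-sample proportion with the following, by vitamin D3 group (active against placebo):

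1. The number and percentage of men with at least one post-baseline corrected calcium above the SAP's existing 2.65 mmol/L threshold, among men with at least one post-baseline sample, with an exact 95% CI.
2. The proportion of men raised at each of 6, 12 and 18 months, with the number sampled at each visit, so that the effect of early stopping can be seen.
3. The pre-treatment value shown separately, with one term (screening or baseline) used for it throughout.

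The same paragraph should name the visits to which the median applies. The cost is a few lines of SAP text and one extra table, with no new samples or visits.
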